1.0 Background

Total pancreas volume is decreased in T1D. Recent studies have demonstrated reduced pancreatic volume is present within months of T1D diagnosis in children, adolescents, and adults [1-4]. As the pancreatic beta cells constitute only 1-2% of the pancreas, the degree of reduction in pancreas volume at disease onset

[figure not shown]

Figure 1. A) Schematic of study design employed to study recent-onset T1D. B) An axial MRI slice through the abdomen of a control participant shows the pancreas (outlined in white). C) An axial MRI slice through the abdomen of a participant with recent-onset T1D shows a smaller, thinner pancreas than seen in the control (outlined in white). D) In the control cohort, pancreas volume correlated with participant weight over the course of adolescent growth. E) Pancreas volume normalized by participant weight, yielding a pancreas volume index in units of [ml/kg], is smaller in participants with T1D than controls. F) Pancreas volume index is unchanged in the control pancreas over a one-year period but declines in participants with T1D over the year after diagnosis. G) When normalized to the baseline measurement for each study participant, pancreas volume increases in the control population but declines in participants with T1D.

suggests exocrine involvement, challenging the established paradigm of T1D being solely a disease of the endocrine pancreas. These unexpected findings raise fundamental questions that challenge our understanding of T1D pathogenesis and point to new questions about management. Especially relevant to the proposed studies, these changes in pancreatic volume and size could reflect deficiency in the exocrine pancreas which could alter food absorption and effect clinical management of glycemia, but this hypothesis has not been investigated.

Our group has developed advanced, standardized approaches to image the pancreas and has applied this approach to understanding the role of whole pancreas pathology in T1D, a disease traditionally thought to only involve the pancreatic islet. An example image of the pancreas of a control participant and participant with recent-onset T1D is shown in Figures 1B and 1C, respectively, with the pancreas outlined in white. Within 100 days of diabetes onset, individuals with T1D (n = 51) had a smaller pancreas (median volume = 29.6 ml) than controls (n = 58, median volume = 47.8 ml, p < 0.001), including when normalized by individual weight (p<0.001). In multiple autoantibody-positive individuals, the pancreas volume was significantly larger than the T1D cohort (p=0.014), but smaller than the control cohort (p=0.019). To account for normal adolescent growth, we compared pancreas volume and weight in control study participants. In the control cohort, pancreas volume correlated with participant weight (Figure 1D, R = 0.76, p < 0.001). Thus, to account for changes in pancreatic volume during normal adolescent growth, pancreas volume was normalized by participant weight yielding what has been termed the pancreas volume index. Normalization by body surface area and BMI were also explored but were inferior to normalizing by weight. At the first study time point, the pancreas volume index was smaller in participants with recent-onset T1D than controls (Figure 1E; median 0.931ml/kg in controls and 0.615 ml/kg in T1D, p < 0.001). Pancreas volume index was smaller in participants with T1D when adjusted for age, sex, and BMI (mean difference -0.279 ml/kg with 95% CI -0.352 to -0.205, p < 0.001 from linear regression). Key data from these early studies are highlighted in Figure 1 and in our published work. As highlighted in Figure 1, pancreas volume declines over the first year after diagnosis (Figure 1F, G). This finding demonstrates the small

Protocol Version #: 6 Protocol Date: 04DEC2023 pancreas in T1D and the presence of an underlying process resulting in ongoing changes in the pancreas after diagnosis with T1D; the physiologic consequences of these changes are not known.

Alterations in exocrine biochemical values in T1D. The significant reduction in pancreas size raises questions as to whether there is also a reduction in exocrine pancreas function. Several studies to date have now demonstrated reductions in key markers of exocrine enzymatic activity. These reductions include abnormalities in fecal elastase and reduced measured in the blood of amylase, lipase, and trypsinogen. The degree of these reductions range from slight deviations from normal to more profound losses of 60% or more. To date there has not been a detailed study of clinical symptoms in patients with T1D to determine whether persons living with T1D have symptoms of pancreatic exocrine insufficiency.

Role of Enzyme Replacement in Diabetes Management. To date there has not been an investigation of the potential for pancreatic enzyme replacement therapy in the management of T1D. Related information can be gleaned from treatment of cystic-fibrosis related diabetes (CFRD) which is characterized by a strong component of exocrine insufficiency related to the CFTR mutation. In individuals with CFRD, enzyme replacement has been shown to reduce post-prandial glycemia excursions, which are reflected in improved GLP-1 responses to mixed meal tolerance testing. As post-prandial excursions and glucose variability are a significant challenge in T1D, how enzyme replacement may impact these parameters is an important question.

2.0 Rationale and Specific Aims

We hypothesize that patients with T1DM who have reduced pancreatic volume will have improved glycemic responsiveness, reduced hypoglycemia, and improved symptoms of pancreatic exocrine insufficiency (PEI) when treated with pancreatic enzyme replacement. To test our hypotheses, we will employ a double-blinded crossover study. This study will be a pilot study to gather preliminary information on potential effect size in preparation for a larger study if supported by these results. The study will enroll approximately 15 adult subjects with T1D who will receive both pancreatic enzyme replacement (Creon) or placebo each for 7 days in a random order. The effect of the intervention will be monitored by continuous glucose monitoring, diet recording, capsule counts, a mixed-meal tolerance test, and a survey to assess symptoms of PEI. This study design will allow for estimation of the effect of pancreatic enzyme replacement on the measured parameters.

Aim 1 will provide preliminary estimates of the effect of enzyme replacement on glucose responsiveness, variability, and hypoglycemia. We will download and analyze CGM data to determine changes occurring in measures of glycemic variability and in the duration and severity of hypoglycemia. Data will be divided into 4 7-day blocks including a run-in period, treatment A, a wash out period, and treatment B. Participants will track their meal composition, report daily exercise duration, and a capsule count will be obtained. At the end of treatment A and treatment B, participants will undergo a mixed meal tolerance test (MMTT) in which glucose, C-peptide, GLP-1, GIP, and glucagon will be measured at defined timepoints.

Aim 2 will provide an initial assessment of the effect of enzyme replacement on symptoms of pancreatic exocrine insufficiency in T1D. We will use the PEI-Q to quantitate symptoms of PEI and their relative change during enzyme replacement at each of the 4 intervals. The frequency and degree of PEI symptoms has not been objectively measured in T1D patients previously.

We will obtain information on the adherence to the intervention and will obtain initial information on median and standard deviation for measured variables that will inform future studies. We will perform a paired t-test to provide an initial assessment of outcomes between groups.

This proposed research will be the first study to determine the effect of enzyme replacement therapy on glycemic variability and patient-reported symptoms or PEI in T1D.

3.0 Animal Studies and Previous Human Studies

There have been no previous animal or human studies of the effects of pancreatic enzyme replacement on glucose regulation in T1D. The reported studies to date, as discussed in the background, strongly support that there is pancreatic volume loss and resultant reduction in exocrine enzymes in T1D. However, the clinical impact of this change is not known; an impact of pancreatic enzyme deficiency and enzyme replacement on glucose tolerance/responsiveness in CFRD has been described.

4.0 Inclusion/Exclusion Criteria

Table 1: Inclusion and Exclusion Criteria

| Inclusion Criteria | Exclusion Criteria |
|--|--|
| Diagnosed with T1DM for at least 12 months Age over 18 Total daily dose of insulin greater than 0.6u/kg/day Current use of a CGM Current use of smart phone Able to read and speak English Willingness and ability to download and provide CGM and pump (if applicable) data Reduction of pancreas volume (<0.6mL/kg BW) | History of celiac disease or inflammatory bowel disease Unwilling to temporarily discontinue use of medication or supplements other than insulin to control blood glucose Pregnant or breast feeding Following a restrictive diet (such as very low carb diet) History of major bowel or bariatric surgery |

5.0 Enrollment/Randomization

- 5.1 Recruitment
 - 5.1.1 Recruitment Resources

We have previously completed a study of over 70 patients with T1D in which they have received one or more MRI studies. This study group allows us to identify patients with significantly reduced pancreas volume for enrollment in this study.

5.1.2 Initial Contact with Potential Participants

Participants will be contacted by telephone. The initial discussion will provide information about the study and assess whether the subject might be eligible to participate in the study. Study personnel will ask the potential subject to confirm his or her:

- Diagnosis of T1DM
- Age
- Weight
- Height
- Diabetes duration
- Medications
- Food preferences and restrictions
- Use of CGM
- Ability to read and speak English

Inclusion and exclusion criteria are listed in table 1. We will invite eligible subjects to participate in the initial screening visit. The initial screening visit will occur at Vanderbilt University Medical Center. The participant will receive an electronic or paper copy of the informed consent document to review prior to the initial screening visit.

5.2 Enrollment

A member of the study team (i.e. key study personnel, KSP) will obtain written, informed consent at the beginning of the screening visit as detailed in section 6.1.1.1. Once consent is obtained, the participant will be enrolled in the study.

5.3 Randomization

Patients will be randomized for order to receive pancreas enzyme replacement or placebo. The Vanderbilt Investigational Drug Services (IDS) pharmacy will do the randomization. They will dispense the randomized capsule bottles for weeks A and B to the study team to be given to the study participants.

5.4 Participant Compensation Participants will receive \$200 for each completed MMTT for a total of up to \$600 for participation in the study.

6.0 Study Procedures

6.1 Research visits

6.1.1 Study Visit 1, Initial Screening Visit

Screening visits will take place in a room designated for research in the Eskind Diabetes Center or in the CRC.

The purpose of the screening visit is to:

- obtain informed, written consent,
- confirm each participant is able to properly upload their continuous glucose monitor (CGM) and pump (if applicable),
- provide participants with blinded treatments (pancreatic enzyme replacement and placebo)
- show participants how to log their food intake on their digital device.

The screening visit will consist of the following:

6.1.1.1 Consent

The PI or designated KSP will obtain consent from all participants. Consent will be obtained in a private room in the Eskind Diabetes Center prior to beginning study procedures. The consent form will be provided to the subject for review prior to the visit. The PI or designated Key Study Personnel will review the consent forms with the participant in detail and provide time for discussing any questions. The study team will provide a copy of the consent form to the participant if applicable.

6.1.1.2 History and Initial Measurements The PI or designee will review each subject's clinical history and take anthropometric measurements (Height/Weight).

6.1.1.3 Nutritional Tracking App Instructions The study team will use a nutritional tracking smartphone application, such as Nutrihand, MyFitnessPal, or FatSecret, on which participants will log their daily caloric intake using the software's web-based or Smartphone app interfaces.

Participants will be asked to track intake using this smartphone app throughout the study.

Participants may be asked to use their personal email to send a CSV file containing data files from the smartphone app to the study team. This CSV file does not contain any PHI. The file will be directly uploaded into REDCap, then the email will be deleted.

6.1.1.4 Continuous Glucose Monitor Instructions

The study team will instruct participants in the use of a continuous glucose monitor (CGM) such as Dexcom G6 or Medtronic Guardian or Freestyle Libre for the monitoring of glycemia during the study. The team will then show T1DM participants how to upload CGM data into a HIPAA and FDA-compliant cloudbased, data-integration platform such as Dexcom Clarity or Tidepool.

6.1.1.5 Insulin Instructions

For participants using insulin pumps, the study team will instruct T1DM participants in the transmittal of data derived from an insulin pump such as Medtronic Minimed 670G, Tandem T-Slim, or Omnipod Insulim Management System. Participants will be encouraged to administer all insulin via insulin pump and enter all carbohydrates consumed into the insulin pump. The team will then show T1DM participants how to upload insulin pump data into a HIPAA and FDA-compliant cloud-based, data-integration platform such as Medtronic Careline or Tidepool. Participants not using an insulin pump wil be asked to record their insulin doses given throughout the day.

6.1.1.6 Randomization and Treatment Plan

Participants will be randomized for order in which enzyme replacement or placebo is received. An equal number of participants will receive either order (A/B or B/A). Participants will receive a range of 50,000-100,000 lipase units per meal (approx. 2 Creon 36,000 capsules) and 25,000-50,000 per snack (1 capsule). The participant will be instructed to take same number of capsules of placebo. Participant and provider will be blinded to capsule assignment.

- 6.1.2 Study visit (baseline)
 - 6.1.2.1 Demographic and history information will be obtained.
 - 6.1.2.2 Participant will be counseled on using and uploading devices and information.
 - 6.1.2.3 Participant will complete a baseline Mixed Meal Tolerance Test (MMTT). The test will be administered according to the well established practices used in the TrialNet clinical T1D research program and described in the included appendix. This baseline visit will take place in the Adult Clinical Research Center (CRC).
- 6.1.3 Study Visit (end of week A)
 - 6.1.3.1 On last day of week A, subject will have an MMTT at the Adult CRC.

6.1.4 Study Visit (end of week B/end of study) This visit will include an MMTT at the Adult CRC and will be scheduled on the last day of week B.

6.1.4.1 History and measurements

Protocol Version #: 6 Protocol Date: 04DEC2023 The PI or designee will review each subject's clinical history and take anthropometric measurements.

6.1.4.2 Continuous glucose monitor and insulin pump data collection

Continuous glucose monitor and insulin pump will be downloaded into a HIPAA and FDAcompliant cloud-based, data-integration platform such as Dexcom Clarity, Medtronic Carelink, or Tidepool.

Information that will be collected from the continuous glucose monitor download will include (but not be limited to):

- Percent of time spent above the glycemic target of 140 mg/dL
- Percent of time spent in the glycemic target of 70 140 mg/dL
- Percent of time spent below the glycemic target of 70 mg/dL
- Percent of time spent in hypoglycemia below 50 mg/dL
- Average blood glucose
- Blood glucose standard variation
- All blood glucose values during the study interval

Information that will be collected from the insulin pump download will include (but not be limited to):

- Average total daily dose of insulin
- Average bolus amount of insulin per day
- Average basal amount of insulin per day

6.1.4.3 Nutritional tracking smartphone application data collection

Information that will be collected from the smartphone app will include (but not be limited to):

- Total number of calories consumed
- Average grams of carbohydrates consumed per day
- Average grams of fat consumed per day
- Average grams of protein consumed per day
- Additional macronutrient data

6.1.4.4 Pancreatic Exocrine Insufficiency Questionnaire

Participants will complete the PEI-Q, a validated measure of PEI symptoms at baseline and at end of Week A and Week B. All surveys will be scored by a member of the research team.

6.1.4.5 Diet Instructions

Patients will be instructed to follow their routine diet.

6.1.4.6 Quality Assurance of Interventions

A capsule count will be performed at end of study to assess adherence to treatment assignment.

6.1.4.7 Mixed Meal Tolerance Test

Subjects will participate in an MMTT at baseline and at end of Week A and Week B. The protocol for the MMTT is described in the Appendix; as a slight modification of the Appendix, an additional 8.5 ml tube of blood will be drawn at each time point.

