Pancreatic enzyme replacement and glucose regulation in Type 1 diabetes

NCT05266963

Statistical Analysis Plan

12/4/2023

Statistical Analysis Plan

NCT05266963 - Pancreatic Enzyme Replacement and Glucose Regulation in Type 1 Diabetes (CREON)

Background

In T1D, there is significant reduction in pancreas volume. The biological impact of this is not known. Because islet cells make up a small fraction of pancreas size, the major reduction in volume is due to loss of exocrine tissue. Since patient with T1D have substantial loss of exocrine tissue and pancreatic enzymes support glucoe regulation and pancreas function, this study tests the hypothesis that pancreatic enzyme replacement will improve C-peptide secretion to regulate glucose excursions and/or will improve symptoms of pancreatic enzorine insufficiency. This document provides additional description of the analysis plan and complements the protocol document where study details are provided.

Primary objective

Aim 1: To assess impact of pancreas enzyme replacement on C-peptide auc in subjects with T1D and reduced pancreas volume

Aim 2: To assess the impact of pancreas enzyme replacement on symptoms of pancreatic exocrine insufficiency (PEI) in T1D.

Secondary Objectives

Secondary assessments will be made to explore mechanisms of effect if the primary outcome is met. These could include analysis of CGM data, measure of circulating hormones and cytokines, assessment of dietary intake.

Trial Design

The study is a single center, double-blinded randomized cross over design in which subjects receive Creon or placebo each for 1 week with a 1 week washout period between.

Eligibility

Inclusion Criteria	Exclusion Criteria
 Diagnosed with T1DM for at least	 History of celiac disease or
12 months Age over 18 Total daily dose of insulin greater	inflammatory bowel disease Unwilling to temporarily discontinue
than 0.6u/kg/day	use of medication or supplements

 Current use of a CGM 	other than insulin to control blood
 Current use of smart phone 	glucose
 Able to read and speak English 	 Pregnant or breast feeding
 Willingness and ability to download and provide CGM and pump (if applicable) data Reduction of pancreas volume (<0.6mL/kg BW) 	 Following a restrictive diet (such as very low carb diet) History of major bowel or bariatric surgery

Treatment

Participants will continue their standard care for diabetes with calculation and adjustment of doses per their primary endocrinologists.

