Participants will receive a range of 50,000-100,000 lipase units per meal (approx. 2 Creon 36,000 capsules) and 25,000-50,000 per snack (1 capsule). The participant will be instructed to take same number of capsules of placebo. Participant and provider will be blinded to capsule assignment.

Assessment of Outcomes

Outcomes will be assessed at baseline and at completion of each treatment week.

Hypothesis

The null hypothesis to be tested is that there will be no difference between the treatment groups.

Blinding

Subjects and investigators will be blinded to treatment assignment. Blinded drug or placebo is provided by the VUMC Investigational Pharmacy.

Analysis

Only subjects completing both arms will be included in the final analysis.

Data collection

Demographics: Participants age, sex, weight will be obtained.

Diabetes Management: Participants estimated or actual insulin dosing, CGM download, diet history, pancreas volume index will be obtained.

Study results: Participants will complete MMTT and PEI questionnaires.

Adherence

Pill counts will be obtained. Participants with significant discrepancy between pill count and diet history may be excluded from analysis.

Primary Outcome Analysis

C-peptide AUC will be calculated from MMTT data. Data from creon and placebo intervals will be compared for each individual in a matched analysis. Comparison will be made by Wilcoxon matched-pairs assessment.

Severity score will be calculated from the PEI-Q survey. Data from creon and placebo intervals will be compared for each individual in a matched analysis. Comparison will be made by t-test

Statistical Software

Analysis will be performed on Prism Ver 10 or on current version of Microsoft excel.

Exploratory Analysis

Additional analyses may be performed if primary endpoint is met to provide mechanistic insight or if requested by journal or editorial review.

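### One end-of-study capsule count cannot date capsule use and can miss swapped or time-shifted use, yet the SAP lets it lead to exclusion

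*Protocol*

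**What the plan says.** **Hand-out.** Protocol 6.1.1 gives as one purpose of the screening visit to "provide participants with blinded treatments (pancreatic enzyme replacement and placebo". Section 5.3 describes separate bottles from the pharmacy: "They will dispense the randomized capsule bottles for weeks A and B to the study team to be given to the study participants". It gives no hand-over time.

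**Schedule.** Protocol 2.0: "Data will be divided into 4 7-day blocks including a run-in period, treatment A, a wash out period, and treatment B". The SAP's Trial Design agrees on the wash-out: "subjects receive Creon or placebo each for 1 week with a 1 week washout period between".

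**End-of-week-A visit.** Protocol 6.1.3 has one item: "On last day of week A, subject will have an MMTT at the Adult CRC". Section 6.1.4.4 adds the PEI-Q at that time point. Neither mentions counting or returning capsules, and no bottle return is described elsewhere.

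**Count.** Protocol 6.1.4.6: "A capsule count will be performed at end of study to assess adherence to treatment assignment". Protocol 2.0 also mentions a count, without a time: "Participants will track their meal composition, report daily exercise duration, and a capsule count will be obtained". The SAP's Adherence section likewise calls for pill counts without a time, and does not say whether they are per bottle.

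**Use of the count.** The same SAP section continues: "Participants with significant discrepancy between pill count and diet history may be excluded from analysis". It sets no threshold.

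**The concern.** As written, participants have both treatments from screening onward, through the run-in, week A, the wash-out and week B. The one count with a stated time comes at the end. It gives a total per bottle at best, and no capsule diary is described that would supply dates. The diet log records food, not capsules.

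Three things depend on capsules being taken in the right week from the right bottle:

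- The SAP's primary comparisons are within-person, Creon against placebo, so a participant who uses the bottles in the wrong order contributes a difference with the wrong sign.
- Protocol 10.1 treats the run-in and wash-out as untreated and compares them to gauge within-person variation. Capsules taken in the wash-out would contaminate that estimate.
- Protocol 2.0 names adherence information as a product of the pilot, and the SAP allows the count to contribute to removing someone from a sample of about 15.

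**Working it through.** The plan gives no figure to reproduce here. The check is a capsule balance, followed by an illustration of what one swap would do.

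**Timing.** With four 7-day blocks, week A ends on day 14 and week B on day 28. The end-of-study visit is on the last day of week B (6.1.4), so the count falls 28 − 14 = 14 days after week A ends.

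**Expected use.** Protocol 6.1.1.6 gives about 2 capsules per meal and 1 per snack. Assumptions not in the documents: 3 meals and 0 to 3 snacks a day, an accurate diet log and a known number dispensed.

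- Per day: 3 × 2 + (0 to 3) = 6 to 9 capsules.
- Per treatment week: 7 × (6 to 9) = 42 to 63.
- Three days' worth: 3 × (6 to 9) = 18 to 27.

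**End-of-study discrepancy.** Capsules used minus capsules expected from the diet log, with the same intake in both weeks:

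| Pattern | Bottle A | Bottle B | Pooled |
|---|---|---|---|
| Bottles fully swapped | 0 | 0 | 0 |
| 3 days of A missed in week A, taken in wash-out | 0 | 0 | 0 |
| 3 days of B taken in wash-out, missed in week B | 0 | 0 | 0 |
| Balanced cross-use, 3 days each way | 0 | 0 | 0 |
| 3 days of week A taken from bottle B, one way | −18 to −27 | +18 to +27 | 0 |
| Full week A plus 3 extra days of A in wash-out | +18 to +27 | 0 | +18 to +27 |

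The first four patterns leave no trace, even with bottles counted separately. The fifth shows only with separate counts. The sixth shows as overuse if the bottle holds spare capsules, which the documents do not state. Neither of the last two can be placed in a particular week.

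**Unequal intake.** With 1 snack a day in week A and 2 in week B, expected use is 7 × 7 = 49 and 7 × 8 = 56. A full swap then gives 56 − 49 = +7 for bottle A and 49 − 56 = −7 for bottle B. So a swap may leave a small mismatch, of a size easily lost in logging error.

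**With a count at the end of week A.** The second pattern would appear that day as a shortfall of 18 to 27 in bottle A, against 0 at the end of study.

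**Illustration of one swap.** If every participant has the same true difference δ and k of 15 have it reversed, the mean is δ × (15 − 2k)/15. For k = 1 this is 13/15 of δ, a loss of 2/15 = 13%. No document gives a swap rate, so this shows the sensitivity of a mean and is not a forecast.

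**The case against.** Several stronger readings are tempting, and the documents do not support them.

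- *Wash-out or wrong-bottle use can never be detected.* Too broad. There are separate bottles (5.3), a diet log kept throughout the study (6.1.1.3) and a planned comparison of count with diet history (SAP, Adherence). One-way errors and net overuse can show, though undated.
- *Every week-A capsule taken in the wash-out passes as adherence.* True only of capsules that replace missed week-A doses. Extra capsules are overuse, which is a discrepancy of the kind the SAP looks for.
- *The pill count decides who is analysed.* The SAP makes exclusion discretionary and bases it on count and diet history together. It also has a separate rule restricting the analysis to those who complete both treatments.
- *Capsules are certain to be counted only once.* This is an inference. Protocol 2.0 and the SAP mention counts without a time, so earlier or per-bottle counts are not ruled out.

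It is also fair to say that this is a small pilot, that no stated figure is wrong, and that no passages contradict each other. The 13% describes a mean difference, whereas the SAP compares C-peptide AUC by the Wilcoxon matched-pairs method.

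These points limit the size of the concern but do not remove it. The only count with a stated time is at the end, both treatments are listed for hand-out at screening, and an undated total cannot distinguish the first four patterns in the table from correct use.

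**Conclusion.** The point holds as a minor, cheap improvement. A single end-of-study count cannot date capsule use. A full bottle swap, or week-A capsules moved into the wash-out, can leave it at or near the expected value, yet the SAP lets a discrepancy lead to exclusion. One-way or net errors may be visible if bottles are counted separately.

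The capsule figures rest on the assumed meal and snack pattern. The 13% rests on one complete swap among 15 and an equal effect in everyone; it is an illustration for a mean and does not transfer directly to the Wilcoxon comparison. How often swaps or time shifts would occur cannot be estimated from the documents.

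**What to change.** - **Protocol 6.1.3:** add that the week-A bottle is counted and taken back at the existing end-of-week-A CRC visit.
- **Protocol 6.1.1:** change the hand-out so that only the week-A bottle is given at the start, and issue the week-B bottle at the end-of-week-A visit.
- **Protocol 6.1.4.6:** keep the end-of-study count for the week-B bottle, and record counts per bottle and per period in REDCap.
- **SAP, Adherence:** state that these per-bottle, per-period counts are the ones compared with the diet history.

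This prevents full swaps and use of bottle A in the wash-out, and dates bottle-A use to the time before the end-of-week-A visit. It does not detect early use of bottle B: that bottle is at home during the wash-out, no visit is described between the wash-out and week B, and a start date on the label would not show when capsules were taken. It also does not supply the exclusion threshold that the SAP leaves open, which is a separate matter.

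The cost is a few minutes at a visit that already takes place and storage of the second bottle by the study team or pharmacy. No visit is added, and no dose or clinical rule changes.
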